Observational Study Information

Title	Real-world comparative effectiveness of stroke prevention in patients with AF treated with Rivaroxaban vs VKA (RELOAD)
Local Project identifier	HEOR0215
IMPACT-No.	18735
Protocol version identifier	2.0
Date of last version of protocol	12 September 2016
Active substance	Rivaroxaban (ATC Code: B01AF01) Phenprocoumon (ATC Code: B01AA04)
Medicinal product	BAY 59-7939; 1912, Rivaroxaban, Xarelto®
Marketing authorization holder(s)	Bayer Healthcare AG, [name], Germany
Research question and objectives	
The aim of this study is to assess the real world comparative effectiveness of Rivaroxaban prescribed in non-valvular atrial fibrillation (NVAf) routine care patients in Germany
 
The primary objective of this study is to assess the risk of ischemic stroke (effectiveness) and intracranial hemorrhage (ICH, safety) in patients treated with Rivaroxaban compared to patients treated with Phenprocoumon
 
The secondary objectives of this study are:
 
 - To assess the cerebral benefit defined as the combined endpoints of ischemic stroke and ICH in patients treated with Rivaroxaban compared to patients treated with Phenprocoumon. - To assess combined effectiveness defined as the endpoints of ischemic stroke, systemic embolism (SE) and transient ischemic attack (TIA) in patients treated with Rivaroxaban compared to patients treated with Phenprocoumon. The components of this combined endpoint will also be analyzed separately.

Country(-ies) of study	Germany
Authors	
[name], Dipl. Oek. Assistant Director Real World Evidence Xcenda GmbH [name], Germany [contact]
 
[name] Manager Real World Evidence Xcenda GmbH [name], Germany [contact]
 
[name] Real Life Evidence Expert Bayer Business Services GmbH [name], Germany [contact] E-mail:[contact]

The study will be conducted in compliance with the protocol and any applicable regulatory requirements.

Throughout this document, symbols indicating proprietary names (®, TM) may not be displayed. Hence, the appearance of product names without these symbols does not imply that these names are not protected.

1. Table of Contents

1. Table of Contents	3
List of Tables.....	4
List of Figures	6
2. List of abbreviations	7
3. Responsible parties.....	8
4. Abstract.....	8
5. Amendments and updates	10
6. Milestones.....	10

Table 28 – Comorbidities after matching	58
Table 29 – Co-medications after matching	59
Table 30 – Standardized Differences before and after matching	60
Table 31 – Primary endpoints after matching.....	60

Table 32 – Composite cerebral benefit endpoint after matching.....	60
Table 33 – Single events of the composite effectiveness endpoint after matching.....	61
Table 34 – Composite cerebral benefit endpoint after matching.....	61
Table 35 – Summary statistics for hospitalizations (overall) after matching	61
Table 36 – Summary statistics of the duration of hospitalizations (overall) after matching.....	61
Table 37 – Co-medications (anticoagulants) after matching.....	62

List of Figures

Figure 1. Selection of the study population.....	15
Figure 2. Study Period and Outcome Variables.....	28

2. List of abbreviations

ATC	Anatomical Therapeutic Chemical Classification System
CCI	Charlson Comorbidity Index
CHA ₂ DS ₂ -VASc	C=Congestive heart failure; H=Hypertension, A=Age (≥75); D=Diabetes mellitus; S=Stroke or TIA or thromboembolism; V=Vascular diseases; A=Age (65-74); Sc=Sex category
CHADS ₂	C=Congestive heart failure; H=Hypertension, A=Age; D= Diabetes mellitus; S= Stroke or TIA
CI	Confidence Interval
DDD	Defined Daily Dose
DESTATIS	Federal Statistical Office
DRG	Diagnosis-Related Group
DVT	Deep Vein Thrombosis
EBM	Einheitlicher Bewertungsmaßstab
EMA	European Medicine Agency
EU	European Union
HRI	Health Risk Institute
ICD-10 GM	International Classification of Diseases, 10th Revision, German Modification
ICH	Intracranial Hemorrhage
INR	International Normalized Ratio
MI	Myocardial infarction
NI	Non-Interventional
NOAC	Non vitamin-K antagonist
NSAID	Non-Steroidal Anti-Inflammatory Drug
NVAF	Non-Valvular Atrial Fibrillation
OAC	Oral Anticoagulants
OPS	International Classification of Procedures in Medicine – German modification (Operationen- und Prozedurenschlüssel)
OS	Observational Study
PAS	Post-Authorization Study
PASS	Post-Authorization Safety Study
PE	Pulmonary Embolism
PZN	National central pharmaceutical number (Pharmazentralnummer)
RR	Relative risk
SAP	Statistical Analysis Plan
SE	Systemic Embolism
SHI	Statutory Health Insurance
TIA	Transitory Ischemic Attack
TIA	Transient Ischemic Attack
UK	United Kingdom
US	United States
VKA	Vitamin K Antagonists
VTE	Venous Thromboembolism

3. Responsible parties

Sponsor	[name] Market Access Manager Bayer Vital GmbH [name] - Germany
Investigator, Statistical Expert	[name], Dipl. Oek. Assistant Director Real World Evidence Xcenda GmbH [name] - Germany
Data Management	[name] Health Risk Institute [name] - Germany

4. Abstract

Title

Real-world comparative effectiveness of stroke prevention in patients with AF treated with Rivaroxaban vs VKA (RELOAD)

Rationale and background

Non-Valvular Atrial fibrillation (NVAf), the most common cardiac arrhythmia worldwide, affects approximately 1-2% of the general population and is a major risk factor for ischemic stroke. Xarelto® (Rivaroxaban) is a Factor Xa inhibitor which is marketed for stroke prevention in patients with NVAf. This study will be conducted to obtain a better understanding on the comparative effectiveness of Rivaroxaban versus Phenprocoumon for stroke prevention in patients with NVAf in a routine care setting.

Research question and objectives

The aim of this study is to assess the real world comparative effectiveness of Rivaroxaban prescribed in non-valvular atrial fibrillation (NVAf) routine care patients in Germany

The primary objective of this study is to assess the risk of ischemic stroke (effectiveness) and intracranial hemorrhage (ICH, safety) in patients treated with Rivaroxaban compared to patients treated with Phenprocoumon

The secondary objectives of this study are:

- To assess the cerebral benefit defined as the combined endpoints of ischemic stroke and ICH in patients treated with Rivaroxaban compared to patients treated with Phenprocoumon.
- To assess combined effectiveness defined as the endpoints of ischemic stroke, systemic embolism (SE) and transient ischemic attack (TIA) in patients treated with Rivaroxaban compared to patients treated with Phenprocoumon. The components of this combined endpoint will also be analyzed separately.

Study design

To address the objectives, this study will be conducted as a retrospective, new user cohort study based on a longitudinal claims database using insurance claims data from the Health Risk Institute's (HRI) research database.

Population

The study population will consist of patients, newly initiated with Rivaroxaban or Phenprocoumon with an NVAf diagnosis from January 1, 2012 through December 31, 2015. Patients will be identified from the HRI research database, a complete longitudinal dataset of patients under statutory health insurance in Germany

Variables

Demographic characteristics, co-morbidities, relevant co-medications, bleeding and stroke risk scores as well as the clinical outcome parameters will be analyzed. The primary outcome parameters are ischemic stroke and ICH; Secondary outcome parameters are the combined endpoints cerebral benefit (ischemic stroke or ICH) as well as combined effectiveness (ischemic stroke, SE or TIA). Single events included in all combined endpoints will be analyzed as part of the secondary objective. Components of ICH (subarachnoid hemorrhage, intracerebral hemorrhage, other and unspecified non-traumatic intracranial hemorrhage) will be assessed separately as well.

Data sources

The study will be conducted using data from the HRI research database. This database includes information about the utilization of services on a case-by-case individual level. To support claims, indications (ICD10-GM) and procedure codes are provided together with costs. The size of the dataset has been reduced to a sample of approximately 4 million patients per year, representative of the German population in terms of age and gender (as of 31.12.2013).

Study size

A preliminary feasibility assessment using the HRI database identified a total of approximately 39,600 treatment naïve users of Phenprocoumon and 22,800 treatment naïve users of Rivaroxaban between Jan 1, 2011 and Sep 30, 2015 being eligible for the planned cohort study.

Data analysis

Patient characteristics will be analyzed descriptively. Incidence rates for the primary and secondary objectives will be estimated as the number of events per 100 person years (% per year). Time-to-event analyses using unadjusted and adjusted multivariate cox proportional hazard models and a 1:1 propensity score matched analyses will be conducted to estimate Hazard Ratios and corresponding confidence intervals.

Milestones

- Final protocol: Oct 15, 2016
- Start of data analyses: Oct 15, 2016
- End of data analyses: Dec 15, 2016
- Final study report: Feb 28, 2017

5. Amendments and updates

This is version 2 of the protocol, modified after initial PRC review in April 2016. Major changes include revising of study objectives and addressing comments of the PRC.

6. Milestones

The following timelines are estimated for the study development, data collection in the database and report of the final study results:

Table 1 – Timelines

Milestone	Planned date
Final protocol	Oct 15, 2016
Start of data analyses	Oct 15, 2016
End of data analyses	Dec 15, 2016
Final study report	Feb 28, 2017

7. Rationale and background

Atrial fibrillation (NVAf) is the most common cardiac arrhythmia, with a prevalence of 1-2% in the general population. NVAf prevalence increases with age (1,2) and is a major risk factor for stroke and death. NVAf confers a 5-fold risk of stroke compared to patients without NVAf patients. The appropriate and timely anticoagulant therapy of patients at risk of stroke is one of the core principles of modern NVAf management (1).

Vitamin-K antagonists (VKA) have long been the standard of care of patients with NVAf. However, narrow therapeutic control, high inter- and intrapersonal variation of VKA exposure, multiple drug and food interactions, the need of extensive monitoring, and the associated risk of bleeding limit their use in practice (3,4).

Rivaroxaban (Xarelto[®]) is a Factor Xa inhibitor which is marketed for stroke prevention in patients with non-valvular atrial fibrillation. The clinical phase III study ROCKET-AF has shown that Rivaroxaban was non-inferior to warfarin for the prevention of stroke or systemic embolism [Patel 2011]. However, all relevant efficacy endpoints showed a trend towards better efficacy (partly significant) of Rivaroxaban compared to VKA in the on-treatment analysis. Regarding safety, a significant reduction in ICH was demonstrated in ROCKET-AF.

Recently conducted observational studies using secondary data sources in Germany (IMS[®] Disease Analyzer) showed significantly better persistence in patients using Rivaroxaban compared to VKA [Evers 2013]. Corresponding results based on claims data in US were published by Laliberté et al. and Nelson et al in 2014 [Laliberte 2014, Nelson 2014].

Similarly, a published comparative effectiveness analysis by Laliberté and colleagues using US claims data suggests a trend towards better effectiveness for most effectiveness endpoints – even though not always significant [Laliberte 2014; Ruff 2014]. One reason for the non-significant findings are the relatively low absolute event numbers of the individual endpoints. Likewise, the NACORA study which was communicated in July 2014 by the French authorities confirmed the favorable trend of Rivaroxaban compared to VKA in the prevention of e.g. ischemic stroke, intracranial hemorrhage, MI. [NACORA 2014] Overall, some publications consistently confirm a trend towards better effectiveness of Rivaroxaban compared to VKA in NVAf in real world. Because of the low event numbers these effects are rarely significant. This trend was also supported by the RELIEF-study that was conducted using German electronic medical records (IMS[®] Disease Analyzer) as well [Coleman 2016].

The aim of this study is to gain further insight into the real world effectiveness and safety profile of Rivaroxaban compared to VKA (Phenprocoumon) prescribed in NVAf patients in Germany. Internationally, Warfarin is the most commonly used VKA whereas in Germany, Phenprocoumon accounts for the majority of VKA prescriptions in NVAf. This retrospective observational database study therefore aims to add insights about the real world effectiveness and safety of Rivaroxaban compared to Phenprocoumon, whose pharmacokinetic profile differs from Warfarin. This study includes the analysis of ICH as a safety parameter and is therefore designated as a Post-Authorization Safety Study (PASS) and is conducted voluntarily by Bayer Vital.

8. Research questions and objectives

The aim of this study is to evaluate the comparative effectiveness of Rivaroxaban versus VKA (Phenprocoumon) in the prevention of ischemic and cerebral events after treatment initiation in NVAf routine care patients in Germany.

8.1 Primary objectives

The primary objective of this study is to assess the risk of the single components ischemic stroke (effectiveness) and ICH (safety) in patients treated with Rivaroxaban compared to patients treated with Phenprocoumon.

Events are defined as hospitalizations with the respective ICD-10-GM diagnosis.

8.2 Secondary objective(s)

The secondary objectives of this study are:

- To assess the cerebral benefit in patients treated with Rivaroxaban compared to patients treated with Phenprocoumon. The combined endpoint is defined as the occurrence of a hospitalization with one of the following diagnoses
 - ischemic stroke
 - ICH
- To assess the real world effectiveness defined as the combined endpoint of ischemic stroke, systemic embolism (SE) and transient ischemic attack (TIA) in patients treated with Rivaroxaban compared to patients treated with Phenprocoumon. The components of this combined endpoint will also be analyzed separately. The composite event is defined as the occurrence of a hospitalization with one of the following diagnoses
 - ischemic stroke
 - systemic embolism
 - TIA

9. Research methods

9.1 Study design

This study will be conducted as a retrospective, new user cohort study based on a longitudinal claims database using German insurance claims data from the Health Risk Institute's (HRI) research database.

New users of Rivaroxaban will be compared with new users of Phenprocoumon to assess the risk for ischemic stroke, ICH, cerebral benefit and the combined effectiveness endpoint of ischemic stroke, SE and TIA.

Strengths of the study design are:

- Study will be conducted using a longitudinal claims data base representing routine care in Germany

- New user design, multivariate adjusted analyses and propensity score matching to reduce and control for confounding

9.2 Setting

The study will include inpatient and outpatient setting as well as drug prescriptions from a sample of German sick funds.

Two study cohorts will be observed:

- NVAF patients who were initiated on Rivaroxaban for stroke prevention
- NVAF patients who were initiated on Phenprocoumon for stroke prevention

9.2.1 Study time frame

The evaluation time frame the study will be January 1, 2011 through March 31, 2016.

For both groups (Rivaroxaban and Phenprocoumon), the date of the first Rivaroxaban or Phenprocoumon dispensing will reflect the index date and mark the beginning of the observation period. Patient baseline characteristics will be measured during the 12 months (365 days, four quarters) preceding the index date (baseline period). The observation (follow-up) period will span from the index date up until the end of data, disenrollment, discontinuation of index treatment (30 day gap period allowed), occurrence of event or switch of treatment.

9.2.2 Selection criteria

The study population will consist of all patients, newly initiated on Rivaroxaban or Phenprocoumon with an NVAF diagnosis meeting the following inclusion and exclusion criteria

Inclusion criteria:

- First dispense date of Rivaroxaban (15mg or 20mg - PZN based) or Phenprocoumon (PZN based) between January 1, 2012 and December 31, 2015
- At least two verified outpatient diagnoses or one inpatient diagnosis (main or secondary diagnosis) of NVAF (ICD-10 GM I48.0/ I48.1/I48.2/I48.9) in the individual time frame of 4 quarters before the index date (pre-index period) or within the index quarter
- Patients will be required to have 4 quarters of enrollment for the assessment of baseline characteristics and be observable and insured in the database for at least one day after their individual index date (post-index period)
- ≥ 18 years of age

Exclusion criteria:

- Patients with valvular AF [4 quarters prior to the index date] (see Table 5)
- Pregnancy [4 quarters prior to index date]

- Malignant cancers [4 quarters prior to the index date or “condition after”] (see Table 10)
- Transient cause of AF [4 quarters prior to index date] (see Table 5)
- Patients with VTE (pulmonary embolism or DVT) [60 days before index] (see Table 10)
- Patients with major surgery defined as hip or knee replacement [60 days before index] (see Table 10)
- Prescriptions of OACs (Rivaroxaban, VKA, Dabigatran, Apixaban) before index date [4 quarters prior to index date] (see Table 3, Table 4)
- Patients receiving more than one anticoagulant substance (Apixaban, Dabigatran, Rivaroxaban or Phenprocoumon) or more than one dosage of a substance on the index date (see Table 3, Table 4)
- *For sensitivity analysis* ([see data analysis section](#)) : Patient with any of the events defined in the combined endpoints [4 quarters prior to index date or “condition after”] (see Table 6)
- Patients with dialysis [4 quarters prior to index date] (see Table 10)

[figure not shown]

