9.3 Variables

9.3.1 Baseline characteristics

Baseline period:

365 days prior to index date for hospital diagnoses and prescriptions and four quarters prior to the index quarter for ambulatory diagnosis. This period will be used to determine whether patients have an NVAF diagnosis, to verify that patients are new users and to assess baseline demographic and clinical characteristics of the patients included in the study population.

The following demographics will be reported for each cohort:

- Gender
- Age
- Age group
 - 18-65, 65-74, ≥ 75

The following clinical characteristics will be reported for each cohort:

- 4-quarter Charlson comorbidity index (CCI)
- CKD, which is important as risk of adverse events among patients receiving NOACs tends to differ according to renal function)
- CHADS₂ score, including Congestive heart failure, hypertension, age, diabetes, stroke
- CHA₂DS₂-Vasc score
- HASBLED score, as measurable without lab values
- Prior non-CNS systemic embolism
- Prior oral anticoagulant use (expected to be 0 with 180-day covariate look back)
- Other relevant co-morbidities:
 - Congestive heart failure
 - DVT
 - Essential hypertension
 - Diabetes mellitus
 - Pulmonary embolism
 - Unstable angina
 - Hyperthyroidism
 - Functional dyspepsia
 - Renal failure

- Other cardiovascular drugs:
 - Antiarrhythmics
 - Beta blockers
 - ACE inhibitors
 - ARBs
 - Calcium channel blockers
 - Diuretics
 - Anti-platelet drug classes
 - NSAIDS

Stroke risk score CHADS₂ and CHA₂DS₂-VASc

Stroke risk scores in the individual pre-index period of 4 quarters before the index quarter with defined risk factors and corresponding ICD-10-GM codes including heart failure, hypertension, age groups, diabetes mellitus, stroke/TIA/embolism, vascular disease and gender (listed in Annex 2, Table 7).

To include Health Care Proxies

- Number of hospitalizations in the baseline period
- Number of unique medications in the baseline period

Comorbidities

Presence of relevant comorbidities e.g. hemorrhagic diathesis due to anticoagulants and antibodies, coagulopathy, hyperthyroidism, etc. (see Annex 2, Table 6) in the inpatient sector (main and secondary diagnoses) or in the outpatient sector (verified diagnoses and in addition “condition after diagnoses” for stroke, bleedings and MI) in the patient’s medical history in the individual pre-index period of 4 quarters before the index quarter will be assessed.

Co-medications

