XARELTO 20 mg Filmtabletten	98	St	10072124
XARELTO 20 mg Filmtabletten	98	St	10852709
XARELTO 20 mg Filmtabletten	98	St	10393644
XARELTO 20 mg Filmtabletten	98	St	4369498

XARELTO 20 mg Filmtabletten	98	St	10200929
XARELTO 20 mg Filmtabletten	98	St	10743802
XARELTO 20 mg Filmtabletten	98	St	10382008
XARELTO 20 mg Filmtabletten	98	St	10999364
XARELTO 20 mg Filmtabletten	98	St	11096612
XARELTO 20 mg Filmtabletten	98	St	11559354
XARELTO 20 mg Filmtabletten	100	St	9333401
XARELTO 20 mg Filmtabletten	10X10	St	9941299

Table 5 – Definition of types of AF

Type of AF	ICD-10-GM code
Paroxysmal	I48.0
Persistent	I48.1
Permanent	I48.2
Typical	I48.3
Atypical	I48.4
Unknown	I48.9

Table 6 – Definition of primary and secondary outcomes

Outcome parameter	ICD-10 GM code	
Primary effectiveness: ischemic stroke	I630, I631, I632, I633, I634, I635, I636, I638, I639	
Primary safety: Intracranial hemorrhage (ICH)	I60.0, I60.1, I60.2, I60.3, I60.4, I60.5, I60.6, I60.7, I60.8, I60.9, I61.0, I61.1, I61.2, I61.3, I61.4, I61.5, I61.6, I61.8, I61.9, I62.00, I62.01, I62.02, I62.09, I62.1, I62.9	
Secondary	combined endpoint cerebral benefit	ischemic stroke and ICH
	systemic embolism (SE) (effectiveness)	I26, I260, I269, I801, I802, I803, I809
	transient ischemic attack (TIA) (effectiveness)	G45.8, G45.9
	combined endpoint effectiveness	ischemic stroke, systemic embolism (SE) and transient ischemic attack (TIA)
	subarachnoid hemorrhage (safety)	I60.0, I60.1, I60.2, I60.3, I60.4, I60.5, I60.6, I60.7, I60.8, I60.9
	intracerebral hemorrhage (safety)	I61.0, I61.1, I61.2, I61.3, I61.4, I61.5, I61.6, I61.8, I61.9
	other and unspecified nontraumatic intracranial hemorrhage (safety)	I62.00, I62.01, I62.02, I62.09, I62.1, I62.9

Table 7 – Definition of stroke risk score CHADS₂ and CHA₂DS₂-VASc

Risk factor	CHADS₂ risk score value	CHA₂DS₂-VASc risk score value	ICD-10-GM code	Description
Heart failure	1	1	I50	Heart Failure
Hypertension	1	1	I10	Essential (primary) hypertension
Age 65-74 years	0	1	-	
Age ≥75 years	1	2	-	

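### The two exclusions that should make the cohort non-valvular cite a table with no such codes, and section 9.2.2 lets an admission after the index date establish AF, against section 9.3.1

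*Protocol*

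**What the plan says.** **Exclusions.** Section 9.2.2 lists "Patients with valvular AF [4 quarters prior to the index date] (see Table 5" and, as a separate criterion, "Transient cause of AF [4 quarters prior to index date] (see Table 5". The table cited in both is headed "Table 5 – Definition of types of AF" in Annex 2.

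**Inclusion.** The same section requires "At least two verified outpatient diagnoses or one inpatient diagnosis (main or secondary diagnosis) of NVAF" with code I48.0, I48.1, I48.2 or I48.9, "in the individual time frame of 4 quarters before the index date (pre-index period) or within the index quarter".

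**Baseline period.** Section 9.3.1 defines it as "365 days prior to index date for hospital diagnoses and prescriptions and four quarters prior to the index quarter for ambulatory diagnosis", and adds: "This period will be used to determine whether patients have an NVAF diagnosis".

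**Follow-up and outcomes.** Under section 9.2.1 follow-up starts at the index date, which is the first dispensing. Under section 9.3.3 every outcome comes from hospital discharge diagnoses in primary or secondary position.

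**Where else the codes could be.** Section 9.7 says that no separate SAP will be written, and Annex 1 lists no stand-alone documents. The protocol is therefore the only place where these definitions can stand.

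**The concern.** The study population is non-valvular AF, and the comparator is a VKA. Of the stated criteria, only the valvular and transient-cause exclusions turn an I48 code into that population. If their codes are not fixed in advance, someone chooses them at the programming stage, with the claims data at hand. Any valve disease left in the cohort would not be handled directly by the Cox adjustment or the propensity score, because Table 2 has no valve covariate.

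The second matter is timing. A new-user cohort should be defined by what is known at the index date. If a hospital stay after that date can supply the AF diagnosis, entry depends on follow-up. In the extreme case a patient enters because of a stroke admission that carries I48 as a secondary code, and that same admission is then counted as the outcome. A comparable patient with no earlier AF record and no admission would not enter at all.

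**Working it through.** **1. The cited table against the exclusions**

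| Item | Content |
|---|---|
| Inclusion codes (section 9.2.2) | I48.0, I48.1, I48.2, I48.9 |
| Table 5 | I48.0, I48.1, I48.2, I48.3, I48.4, I48.9 |
| Valve disease, prosthesis or procedure in Table 5 | none |
| Transient cause in Table 5 | none |

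Four of the six codes in Table 5 are the inclusion codes. The same six rows return in the reporting shells, Tables 18 and 25. Table 5 therefore looks like a descriptive list of AF types and not an exclusion list.

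The other Annex 2 tables do not fill the gap:
- Table 10 has no valve code. It lists hyperthyroidism (E05), but as a comorbidity and without calling it a transient cause of AF.
- Table 8 has I09.9 under congestive heart failure and Z95.8/Z95.9 under peripheral vascular disease. These feed the Charlson index and play no part in selection.

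So no table designates the codes for either exclusion.

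**2. The two windows for AF evidence**

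| Evidence | Section 9.2.2 | Section 9.3.1 |
|---|---|---|
| Inpatient | "4 quarters before the index date (pre-index period) or within the index quarter" | 365 days before the index date |
| Outpatient | same wording | four quarters before the index quarter |

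The index quarter runs on past the index date, and section 9.2.2 sets no cut there. A single later admission therefore qualifies a patient under section 9.2.2 and does not under section 9.3.1. The two AF exclusions look only at the four quarters before index, so inclusion may use post-index data where exclusion may not.

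The structure of the data explains only part of this. Section 9.9 says that outpatient diagnoses are dated by quarter, which is a reason for an index-quarter rule for them. Section 9.4 says that hospital stays carry admission and end dates, so an inpatient cut at the index date is feasible.

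**3. Scale of the second matter**

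The protocol gives no figure to reproduce. Inputs for an upper bound:
- Patients (section 9.5): 17,000 + 30,000 = 47,000.
- Ischemic-stroke rates (section 9.5 power table): 0.0054 to 0.0134 per year.
- Index dates: assumed evenly spread over 1 January 2012 to 31 December 2015 (1,461 days). The index quarter then extends 0 to 91 days past the index date, with a mean of 45.16 days. On 98.9% of possible index dates at least one such day remains.
- All patients assumed to stay at risk to the end of the index quarter.

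Person-time = 47,000 × 45.16 / 365.25 ≈ 5,811 person-years.

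Expected stroke admissions = person-time × rate:
- 5,811 × 0.0054 ≈ 31
- 5,811 × 0.0134 ≈ 78

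These are all stroke admissions in the window. The number that matters is the subset with no AF evidence before the admission, and the protocol does not give that share.

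**The case against.** **On the exclusions.** Both are stated in words, and the reference to Table 5 is so plainly wrong that nobody would run it. A programmer would ask, and a sensible list would be found. That is fair, and it limits the consequence: the defect is a missing pre-specification, and nothing shows that valve patients were kept. A reader might infer that the criteria remove nobody, or every AF patient, or only those with I48.3 or I48.4. Each is a literal reading of an unusable reference, and the document does not show that any was meant.

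**On bias from valve disease.** A reader might infer a shift in the hazard ratio. If 5% to 10% of phenprocoumon starters and no rivaroxaban starters had valvular AF at twice the event rate, a true ratio of 1.00 would become 1/1.05 = 0.95 to 1/1.10 = 0.91. At 1.5 times the rate it would be 1/1.025 = 0.98 to 1/1.05 = 0.95. None of these inputs is in the protocol. The sum also ignores matching and adjustment on heart failure, comorbidity indices, hospitalizations and medications, which may absorb part of any excess. It is not evidence of a bias of that size, or of any bias.

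**On the window.** Section 9.3.1 gives a rule under which the problem does not arise, so it would be too strong to say that the plan admits patients through their outcome. The rule is also the same in both arms, and no direction of bias can be shown. What stands is that the two sections disagree and that section 9.2.2, where eligibility is defined, holds the version that uses follow-up.

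**On index-quarter outpatient codes.** One could go further and demand an AF code from an earlier quarter. That would drop patients who were diagnosed and started on treatment in the same quarter, a natural group in a new-user cohort. The document does not support a claim that this loss is small.

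**Conclusion.** Both parts hold on the text and need no assumed figure.

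1. The valvular and transient-cause exclusions have no operational definition anywhere in the protocol, and the protocol rules out a separate SAP. They cannot be run as written.
2. Sections 9.2.2 and 9.3.1 contradict each other on when AF must be documented. As section 9.2.2 stands, an inpatient code recorded after index, including one on the outcome admission, can decide entry.

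The size and direction of any bias cannot be derived from the document. For the second part, about 31 to 78 stroke admissions is a ceiling. It rests on the planned cohort sizes, the rates in the power table, evenly spread index dates and everyone remaining at risk. The number of patients who qualify only through such an admission is smaller. The point should be settled before the analysis because the repair is cheap and the rule decides who is in the cohort.

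**What to change.** - **Exclusions.** Replace both references to Table 5 in section 9.2.2 with explicit ICD-10-GM and OPS code lists, one for valvular AF and one for transient causes, fixed before the cohort is built. Keep Table 5 as the descriptive list of AF types.
- **Inpatient AF evidence.** Reconcile sections 9.2.2 and 9.3.1 by counting only hospital stays that ended on or before the index date.
- **Outpatient AF evidence.** Keep index-quarter codes, since only the quarter is known, state the rule identically in both sections, and add a sensitivity analysis that leaves these codes out.

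The cost is two code lists, one date filter on stays that are already dated, and one further sensitivity run. Patients whose only AF evidence is a post-index admission would be lost. That loss should be small, but the protocol gives no figure for it, so the report should state the count.
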